## 6.2

### **Blinding**

All subjects and clinical staff (except for the unblinded pharmacy staff) will be blinded to treatment. An unblinded pharmacy staff will be required at the Clinical Site to comply with the study's randomization and blinding requirements. At the Clinical Site, prior to study initiation, the Principal Investigator will be responsible for designating a qualified pharmacy staff to serve as the unblinded pharmacy staff in the study. Unblinded pharmacy staff may dose subjects but may not participate in any subject assessments.

Throughout the study, the designated unblinded pharmacy staff will be responsible for all drug accountability issues, including preparing, labeling, dispensing, and dosing study drug according to the randomization code provided, yet remain independent of all subject assessments. The pharmacy staff will follow the Standard Operating Procedures and Work Instructions related to pharmacy services and protocol-specific requirements.

Randomization codes will be provided to the unblinded pharmacy staff. Confirmation of receipt of the randomization code will be required by the Sponsor. The unblinded pharmacy staff will be responsible for maintaining the blind, consistent with protocol design, throughout the study. All documentation is to be filed in the Pharmacy Manual. Access to this manual by study personnel will be restricted to the unblinded pharmacy staff.

The subjects, Principal Investigator, and all other study personnel involved with subject assessments will remain blinded to the actual treatment assignments of the subjects. The Principal Investigator will be ultimately responsible for ensuring that the integrity of the blind is maintained throughout the study and will be required to notify the Sponsor in the event of any breaking of the blind for any reason.

Note: The blinding rules and procedures described in the protocol do not apply to the unblinded repeat cohort using a different dosage formulation; see Appendix 5.

**6.2.1 Clinical Research Staff**

All observers who evaluate any reported AE, laboratory abnormalities, ECGs, and changes in the ECGs will be blinded as to what treatment sequence each subject is assigned.

**6.2.2 Study Subjects**

All subjects will be blinded as to which treatment they are receiving at any dose.

**6.2.3 Bioanalytical Laboratory**

All samples will be sent to the bioanalytical laboratory for analysis. The bioanalytical laboratory will be unblinded and only run the analysis on active treatment subjects.

**6.2.4 Pharmacokinetic Analysis**

Pharmacokinetic analysis will be completed only on the active treatment subjects and will be blinded by subject for interim assessments.

**6.2.5 Cardiac Vendor**

Electrocardiogram data will be analyzed in a blinded fashion and then unblinded by the cardiac vendor in order to be presented by treatment group in aggregate (reviewers will remain blinded by subject).

**6.2.6 Unblinding Procedures**

Unblinding of cohort data will occur after completion of the final subject study visit and follow-up telephone call for the cohort.

The treatment assignment should be unblinded at the clinic only in the case of an emergency, when knowledge of the study drug assignment is absolutely necessary for the clinical management or welfare of the subject. Breaking of the blind at the clinic under any other circumstances will be considered a protocol violation.

The Investigator is strongly encouraged to contact the Sponsor before unblinding the study drug assignment prior to the scheduled assessment of tolerance and safety data. If the blind is broken for any reason, the Investigator must notify the Sponsor within 1 day, and an SAE form must be completed, if appropriate. In addition, the Investigator will record the date and reason for revealing the blinded study drug assignment for that subject in the source documents and appropriate CRF page(s).

**6.3 Check-In Procedures**

Subjects will check into the clinic on Day -2 for Part 1 and Day -1 for Part 2.

At check-in, all subjects will be evaluated to confirm they continue to meet all the inclusion criteria (Section 5.1) and none of the exclusion criteria (Section 5.2).

Subjects will undergo the following assessments during the confinement period prior to dosing:

- Physical and neurological examinations
- Weight
- Vital signs (temperature, respirations, blood pressure, pulse, and pulse oximetry)
- Triplicate 12-lead ECG
- Clinical laboratory tests
- Urine drug, alcohol, and cotinine screens – results must be negative for the subject to continue study participation
- Serum pregnancy test (all female subjects) – results must be negative for the subject to continue study participation
- Concomitant medication review
- AE review
- Cardiac telemetry (Part 1 only)

#### **6.4 Confinement**

Part 1 fasting cohorts, and Part 2, Cohort 8, Arm 4 only: Subjects will be admitted to the research center on Day -2 (Part 1) or Day -1 (Part 2) and remain confined until after completion of the 48-hour procedures on Day 3. Subjects will return for a follow-up visit approximately 72 hours after dosing (Day 4) and receive a follow up phone call on Day 11 (+1 day).

Part 1 food-effect cohort, Part 2, Cohort 8, Arms 1-3 and Cohort 9: Subjects will be admitted to the research center on Day -2 of Period 1 and Period 2 (Part 1) or Day -1 (Part 2) and remain confined until after completion of the 48-hour procedures on Day 3 of each study period. Subjects will return for a follow-up visit approximately 72 hours after dosing (Day 4) in each study period. Subjects will receive a follow up phone call on Day 11 (+1 day) of Period 2.

Please note that Cohort 9 is the same 6 subjects that were in Cohort 8, Arm 4 (IR tablet formulation) under fed conditions. In Cohort 8, Arm 4, subjects fasted.

#### **6.5 Fasting/Meals/Beverages**

##### **6.5.1 Fasting/Meals**

Part 1 fasted cohorts and Part 2, Cohort 8, Arm 4 only Optional meals (lunch, snack, and dinner) may be served the day of check-in. All subjects will then be required to fast for at least 10 hours before dosing. The subjects will fast for 4 hours after dosing. Standard meals will be provided at appropriate times after dosing.

Part 1 food-effect cohort, Part 2, Cohort 8, Arms 1-3 and Cohort 9: Optional meals (lunch, snack, and dinner) may be served the day of check-in.

In the fasting study period, all subjects will be required to fast overnight for at least 10 hours before dosing.

In the fed study period of Part 1 and Part 2 (Cohort 8, Arms 1-3 and Cohort 9) subjects will be required to fast for at least 10 hours overnight before consuming a required FDA standard high-fat, high-calorie breakfast. Subjects will receive the required FDA standard high-fat, high-calorie breakfast to begin 30 minutes prior to scheduled administration of the dose and to end (last bite taken) within 5 minutes prior to dosing. The subjects will fast for 4 hours thereafter. The following high-fat (approximately 50% of total caloric content of the meal), high-calorie (approximately 1000 calories) breakfast will be ingested 30 minutes prior to administration of the drug:

- 2 eggs fried in butter
- 2 strips of bacon
- 2 slices of toast with butter
- 4 ounces of hash brown potatoes
- 8 ounces of whole milk

This meal contains approximately 150 protein calories, 250 carbohydrate calories, and 500-600 fat calories. An equivalent meal may be substituted with documentation of the menu and caloric contents with Sponsor approval prior to administration of the meal.

Subjects will fast for 4 hours after dosing. Standard meals will be provided at appropriate times after dosing.

Please note that Part 2, Cohort 9 is the same 6 subjects that were in Cohort 8 Arm 4 (IR tablet formulation) under fed conditions. In Cohort 8 Arm 4, subjects fasted.

#### 6.5.2 Beverages

Each dose of TBI-223 oral suspension and placebo for TBI-223 oral suspension will be administered orally followed by approximately 200 mL of room temperature water.

Except for the room temperature water provided with the study treatment, no water may be consumed for 1 hour prior to each dose through 1 hour after each dose.

At other times, subjects will be encouraged to drink water ad libitum.

### 6.6 Drug Administration

#### 6.6.1 Administration of oral care strips

Listerine® oral care strips (or similar product) will be used to blind subjects to treatment (TBI-223 Oral Suspension or placebo for TBI-223 oral suspension). One strip will be added to the subject's tongue immediately before administration of the study treatment. Another strip will be placed on the subject's tongue immediately after the subject has swallowed the study treatment and 200 mL of water. Research staff will place the strip on the midsection of the subject's tongue. The subject should keep the strip on the

tongue while it dissolves but may swallow when they feel the need to. A mouth check will be performed, using a flashlight and tongue depressor, after each administration of Listerine oral care strip to ensure that all of the film has been dissolved.

6.6.2 Administration of TBI-223 Oral Suspension or Placebo for TBI-223 Oral Suspension

*Note: Detailed instructions for preparing and dispensing TBI-223 will be provided in a separate pharmacy manual. Any instructions in the pharmacy manual shall supersede those presented in this protocol.*

TBI-223 Oral Suspension or placebo for TBI-223 oral suspension will be transferred and stored in Pyrex glass reagent bottles with a polypropylene (PP) screw cap without a liner. These bottles will be used for mixing, sampling, and storage prior to administration.

The required doses of the drug product will be dispensed using commercially available oral syringes of suitable capacity. The suspension will be dispensed just prior to dosing and not stored in the oral syringes.

Each dose of TBI-223 will be administered orally followed by approximately 200 mL of room temperature water. A mouth check will be performed immediately after dose to ensure that the medication has been appropriately swallowed.

Subjects will remain seated, except as otherwise required for study procedures or personal needs, for the first 4 hours after dosing. Should the need to move about occur during the first 4 hours after dosing on these days, subjects may be escorted to such procedures or activities by research personnel as deemed medically necessary. Subjects will not be allowed to lie down, except as directed by clinical staff secondary to AEs, for the first 4 hours after dosing.

6.6.3 Administration of TBI-223 Sustained Release and Immediate Release Tablets

For Part 2, Cohort 8 and Cohort 9, each subject will receive the oral dose of the assigned study treatment (TBI-223 SR tablet formulations [Prototypes 1, 2, or 3] or TBI-223 IR tablet formulation) with approximately 240 mL (8 fl. oz.) of room temperature water. Subjects must swallow the study medication intact. The medication should NOT be crushed or chewed. A hand and mouth check will be performed immediately after dose to ensure that the medication has been appropriately swallowed.

The subjects will remain seated, except as otherwise required for study procedures or personal needs, for the first 4 hours after dosing. Should the need to move about occur during the first 4 hours after each dose, subjects may be escorted to such procedures or activities by research personnel as deemed medically necessary. Subjects will not be allowed to lie down, except as directed by clinical staff secondary to AEs, for the first 4 hours after dosing.

## 6.7 Blood Sampling, Processing and Shipment

Blood samples will be collected as detailed in Appendix 1.

Refer to the Schedule of Events for specific blood collection time points. The Principal Investigator, in conjunction with the Sponsor, may collect additional blood if necessary for repeat laboratory or safety evaluations including AE follow-up.

### 6.7.1 Part 1 fasting cohorts, and Part 2, Cohort 8, Arm 4 only

A total of 80 mL (20 x 4 mL samples) will be collected for pharmacokinetic analysis from each subject. Approximately 51.5 mL of blood will be collected for the clinical laboratory evaluations and coagulation testing. The total volume of blood collected from each subject will not exceed approximately 131.5 mL.

**Table 4 Total Volume of Blood to be Collected for Testing: Fasting Cohorts**

Reason for Collection	Number of Samples	Volume per Sample (mL)	Total Volume (mL)
Clinical labs at screening	1	12.5	12.5
Clinical labs during study (check-in, 24 and 72 hours/end-of-study)	3	8.5	25.5
Coagulation	5	2.7	13.5
Pharmacokinetic analysis	20	4.0	80.0
		Total	131.5

### 6.7.2 Part 1 food-effect cohort, Part 2, Cohort 8, Arms 1-3 only, and Cohort 9

A total of 160 mL (40 x 4 mL samples) will be collected for pharmacokinetic analysis from each subject. Approximately 90.5 mL of blood will be collected for the clinical laboratory evaluations and coagulation testing. The total volume of blood collected from each subject will not exceed approximately 250.5 mL.

Please note that Part 2, Cohort 9 is the same 6 subjects that were in Cohort 8 Arm 4 (IR tablet formulation) under fed conditions. In Cohort 8 Arm 4, subjects fasted.

**Table 5 Total Volume of Blood to be Collected for Testing: Food-effect Cohorts**

Reason for Collection	Number of Samples	Volume per Sample (mL)	Total Volume (mL)
Clinical labs at screening	1	12.5	12.5
Clinical labs during study (check-in, 24 and 72 hours/end-of-study)	6	8.5	51.0
Coagulation	10	2.7	27.0
Pharmacokinetic analysis	40 (20 in each study period)	4.0	160.0
		Total	250.5

### 6.7.3 Pharmacokinetic Sampling Time Windows

Blood samples collected within the time windows listed below will not be considered deviations. Note: For the food-effect cohort, time windows are relative to dosing in each study period.

**Table 6 Acceptable Pharmacokinetic Sampling Time Windows**

Investigation and examination	Allowable Time Window		
	Postdose*		
	≤24 hours	>24 hours to ≤48 hours	>48 hours
Plasma sample collection for pharmacokinetic assessment	± 2 minutes	± 5 minutes	± 10 minutes

For the food-effect cohort, time windows are relative to dosing in each study period.

### 6.8 End-of-Study Procedures

On the day of study discharge (Day 4), the following procedures will be conducted:

- Physical and neurological examinations
- Vital signs measurements (blood pressure, pulse, temperature, respirations, and pulse oximetry)
- Blood collection for hematology, chemistry, coagulation
- Urine collection for urinalysis
- Concomitant medication review
- AE assessment

Subjects will receive a follow up phone call (Day 11 [+1 day]).

For the food-effect cohort, the timing of these assessments is relative to study period 2.

## **6.9 Safety Monitoring and Procedures**

### **6.9.1 Adverse Events**

Subjects will be instructed to inform the study physician and/or research personnel of any AEs that occur at any time during the study. Subjects will be monitored for AEs from the first dose through the end-of-study visit.

Refer to Section 7 for details regarding AE reporting.

### **6.9.2 Clinical Laboratory Evaluations**

Clinical laboratory evaluations will be performed at the times noted on the appropriate events schedule ([Table 9](#)), A Clinical Laboratory Improvement Amendments (CLIA) certified laboratory will perform all clinical laboratory tests for this study. If exclusionary lab criteria are met, values may be confirmed by repeat evaluation.

- Hematology: hemoglobin, hematocrit, total and differential leukocyte count, red blood cell count (RBC), and platelet count.
- Serum Chemistry: albumin, blood urea nitrogen (BUN), creatinine, total bilirubin, alkaline phosphatase (ALP), aspartate transaminase (AST), alanine transaminase (ALT), sodium (Na+), potassium (K+), chloride (Cl), lactate dehydrogenase (LDH), calcium (Ca), uric acid, glucose, gamma-glutamyltransferase (GGT), and magnesium.
- Serology: hepatitis B surface antigen, hepatitis C antibody, and HIV.
- Coagulation: prothrombin time (PT), partial thromboplastin time (PTT), and international normalized ratio (INR).
- Urinalysis - The following will be evaluated by an automated or manual urine “dipstick” method: pH, specific gravity, protein, glucose, ketones, bilirubin, blood, nitrite, leukocyte esterase, and urobilinogen. If protein, occult blood, nitrite, or leukocyte esterase values are out of range, a microscopic examination will be performed.
- Urine Drug, Cotinine, and Alcohol Screens: drugs of abuse (amphetamines, benzodiazepines, barbiturates, cannabinoids, cocaine, opiates), alcohol, and cotinine.
- Pregnancy test (all female subjects).
- Follicle-stimulating hormone (female subjects claiming post-menopausal status).

### 6.9.3 Vital Signs

Vital signs (blood pressure, pulse rate, and respiration rate, pulse oximetry, and temperature) will be measured performed at the times noted on the appropriate events schedule ([Table 9](#)).

NOTE: Blood pressure and pulse rate will be noted and collected at the same time.

For purposes of qualifying any given subject for study participation, out-of-range vital signs may be repeated once.

Predose vital signs will be assessed by the Principal Investigator or designee (e.g., a medically qualified Sub-Investigator) prior to each study drug administration. The Principal Investigator or designee will verify the eligibility of each subject with out-of-range vital signs and document approval prior to dosing.

Additional vital signs measurements may be performed as deemed medically necessary by research personnel.

Blood pressure and heart rate should be measured after subjects are in a seated position for at least 2 minutes and then again after standing for at least 1 minute, except when they are supine or semi-reclined because of study procedures and/or AEs, or as deemed necessary by the Investigator.

### 6.9.4 Physical Examinations

Physical examinations, including height and weight measurements, will be conducted at the times noted on the appropriate events schedule ([Table 9](#)).

### 6.9.5 Neurological Examinations

Detailed neurological examinations will be conducted at the times noted on the appropriate events schedule ([Table 9](#)) and at unscheduled time points as deemed necessary by the Investigator. Each neurological exam will assess the following:

- Mental Status – orientation, speech, and memory
- Cranial Nerves – excluding fundoscopic examination
- Muscle tone and strength
- Sensory System – brief survey for light touch and temperature of the face, neck, arms, trunk, and legs
- Reflexes –deep tendon reflexes and plantar responses (Babinski sign)
- Coordination – upper and lower extremities, including tremor
- Gait – tandem gait

#### 6.9.6 12-Lead Electrocardiograms

Safety 12-lead ECGs will be recorded and printed for on-site review by the Principal Investigator or designee at the times noted on the appropriate events schedule ([Table 9](#)). The interpretation of these ECGs will be noted, but not the ECG intervals, unless as part of an AE (e.g. 1st degree AV block with PR interval of 240 msec).

All safety ECGs will be performed after the subject has been in supine position for a minimum of 5 minutes.

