#### 1.4 Adverse Effects, Warnings, and Precautions

TBI-223 has not been tested in humans, therefore its potential adverse effects are unknown. The following adverse reactions were noted in more than 1% of adult subjects in a study of different drug in the oxazolidinone class, linezolid (marketed as Zyvox®): headache, diarrhea, nausea, vomiting, dizziness, rash, anemia, taste alteration, vaginal and oral candidiasis, abnormal liver functions tests, fungal infection, tongue discoloration, and abdominal pain.

The Zyvox® label carries warnings and precautions for myelosuppression, peripheral and optic neuropathy, serotonin syndrome, *Clostridium difficile* associated diarrhea, elevated blood pressure in patients with hypertension, lactic acidosis, convulsions, hypoglycemia, and development of drug-resistant bacteria.

Given the key safety findings in the nonclinical safety studies for the cardiovascular system (prolonged QTc) and the nervous (CNS) system (tremors), we will implement the following monitoring procedures.

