### **Cardiovascular Monitoring**

Cardiovascular monitoring will be conducted and include the following at both protocol-defined time points and whenever deemed necessary by the study investigator. Subjects treated with TBI-223 will have their ECGs evaluated prior to treatment and during treatment. During treatment, the timing of ECGs will be guided by pharmacokinetic (PK) data so that collection occurs around the estimated  $T_{max}$ .

ECGs will be interpreted and signed and dated by the Principal Investigator or designee. The ECGs will be classified as normal, having a clinically insignificant abnormality, or having a clinically significant abnormality. All clinically significant abnormalities will be recorded as AEs. In addition, ECG parameters of ventricular rate, PQ or PR interval, QRS duration, and QT interval (corrected and uncorrected) will be noted on the case report form (CRF). If a patient's corrected QT interval (QTcF) exceeds 500 msec while on treatment or there is a change from baseline exceeding 60 msec, TBI-223 administration should be stopped, and the patient monitored with ECGs and/or telemetry until the QTcF returns to pre-treatment levels.

Study subjects will also be monitored with Holter monitoring. Holter monitoring will begin approximately 24 hours prior to and continue until 48 hours after dosing.

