**Table 2 Actual Dose Cohorts for Part 1**

Cohort a (Group b )	Dose c
1 (sentinel group)	Single dose of 50 mg TBI-223 (n=2)
1 (remainder of cohort)	Single dose of 50 mg TBI-223 (n=4)
2 (Group 1)	Single dose of 100 mg TBI-223 (n=3)
2 (Group 2)	Single dose of 100 mg TBI-223 (n=3)
3a (Group 1)	Single dose of 300 mg TBI-223 (n=3)
3a (Group 2)	Single dose of 300 mg TBI-223 (n=3)
3b (Capsule cohort)	Single dose of 300 mg (TBI-223 in oral enteric capsules) (n=4)
4 (Group 1)	Single dose of 600 mg TBI-223 (n=3)
4 (Group 2)	Single dose of 600 mg TBI-223 (n=3)
5 (Group 1)	Single dose of 1200 mg TBI-223 (n=3)
5 (Group 2)	Single dose of 1200 mg TBI-223 (n=3)
6 (Group 1)	Single dose of 2000 mg TBI-223 (n=3)
6 (Group 2)	Single dose of 2000 mg TBI-223 (n=3)
7 (Group 1)	Single dose of 2600 mg TBI-223 (n=3)
7 (Group 2)	Single dose of 2600 mg TBI-223 (n=3)

mg = milligram; n = number of subjects.

- a) Additional cohorts may be enrolled if deemed appropriate by the Sponsor to repeat a dose level or to study another dose level or another dosage formulation.
- b) Dosing between Groups 1 and 2 to occur at least 24 hours apart.
- c) Subjects will be dosed under fasted conditions. One of the dose cohorts will be selected to return for an additional dose under fed conditions.

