#### Dose Escalation Review

A review period will take place after the dosing of all subjects in each cohort in order to evaluate and interpret all pharmacokinetic and safety data collected.

The review of all pertinent safety/tolerability data will include physical and neurological examinations, ECGs, vital signs, clinical laboratory tests, cardiac monitoring, and AEs or serious adverse events (SAEs) through Day 4. Also, data from the current dose cohort and all previous cohorts will be considered.

The Sponsor and Investigator will determine if there are sufficient data available from all subjects to make a dose escalation decision. Any AEs of grade  $\geq 2$  toxicities (per Division of Microbiology and Infectious Disease [DMID] toxicity table; Appendix 3) must be considered in the decision to escalate to the next dose level. ECG data will be analyzed in a blinded fashion and unblinded by ECG vendor in order to be presented by treatment group in aggregate (reviewers will not be unblinded by subject).

Pharmacokinetic analysis will be completed only on the active treatment subjects and will be blinded to subject. Blinding will also extend to others who are intimately involved with the study except for the designated unblinded pharmacy staff and in cases of medical emergencies.

Upon review of relevant cohort data, the Sponsor, in conjunction with the Investigator may decide to:

- 1: Escalate the dose as planned
- 2: If concerns arise from pharmacokinetic and safety data that do not warrant ceasing escalation:
  - a: evaluate an intermediate dose level prior to the next planned dose level;

OR

- b: repeat a given dose level in a new cohort of subjects
- c: Repeat a dose level using a different dosage formulation.

3. Add a cohort or increase the dose of the next cohort if the bioavailability is lower than expected in the previous cohort and there were no safety concerns.
4. Halt the study.

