### **3.2 Stopping Rules for Cohorts**

If any of the cohort stopping rules are met, cohort dosing must be stopped until review of the data by the Sponsor and the Investigator.

Rules for stopping dosing of a cohort include the following:

1. Two or more subjects experience drug-related SAEs;
2. Two or more subjects experience grade 2 or higher (per DMID toxicity table; Appendix 3) central nervous system (CNS) AEs considered related to drug.
3. Two or more subjects develop drug-related QTcF prolongation greater than or equal to 500 msec or a change from baseline greater than 60 msec, after completing repeat testing.
4. Two or more subjects experience drug-related Grade 3 or Grade 4 cardiac rhythm cardiac disturbances.

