#### 6.9.7 Cardiac Holter Monitoring, and Cardiodynamic Assessment

In order to detect potential changes in ECG parameters, study subjects will undergo cardiac Holter monitoring. Holter monitoring will begin approximately 24 hours before dosing and continue for at least 48 hours after dosing.

On Day -2 and Day -1, subjects should fast until lunch to avoid circadian fluctuations.

In addition, replicate ECGs will be obtained after dosing, specifically around the estimated Tmax (which is estimated to be around 3 hours after dosing; although the timing may be altered based on generated phase 1 pharmacokinetic data). ECG data will be analyzed focusing in particular on changes of the QT segment although other ECG parameters will be analyzed, as specified in the Statistical Analysis Plan (SAP).

Continuous 12-lead ECGs (Holter) will be recorded for 24 hours prior to dose and for at least 48 hours post dose. The ECG waveforms will be stored for analysis as appropriate after the completion of the study. Replicate 12-lead ECGs will be extracted prior to dosing and serially after dosing by the central ECG laboratory at the time points shown in Table 9. At each time point for ECG extraction, subjects should be resting in the supine position for at least 10 minutes.

NOTE: When ECG extractions coincide with safety ECGs, vital signs assessment and blood draws, procedures should be carried out in said order.

Details regarding the equipment and methods to be used for continuous Holter extraction and analysis are provided in Appendix 4.

Part 2 of the study will not have cardiac Holter monitoring.

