- c. A detailed neurological exam will be conducted by a licensed physician or suitably medically qualified designee at both scheduled and unscheduled time points as deemed necessary by the Investigator. The neurological examination is planned to be performed around the estimated  $T_{max}$  (currently estimated at 3 hours post dosing; this time could change based on data generated during the study). Timepoints can be altered based on generated PK data.
- d. Vitals signs will be measured at screening, check-in, and while subjects are in confinement. Vitals signs will be measured within 90 minutes prior to dosing and within 15 minutes of the remaining defined time points in flowchart. Both blood pressure and heart rate (pulse) should be captured simultaneously. Blood pressure and heart rate should be measured after subjects are in a seated position for at least 2 minutes and then again after standing for 1 minute, except when they are supine or semi-reclined because of study procedures and/or AEs, or as deemed necessary by the Investigator.
- e. 12-lead safety ECGs will be printed and reviewed on-site by the Principal Investigator or designee. TriPLICATE ECGs will be completed at screening, Day -2, Day -1, and at 48 hours only. All other time points will be single ECG readings within 15 minutes at time points within flowchart. The predose ECG should be performed prior to the pre-dose blood draw. If a subject experiences a post-dosing QTcF  $>500$  msec or a change-from-baseline QTcF  $>60$  msec, after repeat testing, additional ECGs should be recorded until normalization or return to baseline.
- f. The first ECG may be done within 2 hours prior to dosing and must be completed 20 minutes prior to the pre-dose blood draw. All safety ECGs on Day 1 and Day 2 will be extracted from a continuous 12 lead Holter recording at discrete timepoints as noted in above flow chart and Day -1 will be extracted at the same time as vital sign measurements.
- g. Subjects will be monitored for treatment-emergent AEs from the time of dosing and throughout the study via safety assessments, observation, and subject reporting. A specific inquiry regarding AEs will be conducted prior to dosing and at time points determined by the Investigator postdose and upon return to clinic for subsequent visits. The inquiry to collect AEs using non-leading questions on Day 11 ( $\pm 1$  day) will be done via a phone call.

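### Protocol 6.9.6 leaves safety-ECG intervals unrecorded unless part of an AE, against Protocol 1.4 and the SAP's planned interval tables; Part 2 and capsule Cohort 3b have no Holter to fall back on

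*Protocol*

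**What the plan says.** **Protocol 6.9.6** has the investigator or designee review printed safety ECGs on site and then limits what is kept: "The interpretation of these ECGs will be noted, but not the ECG intervals, unless as part of an AE". It points to Table 9, the Part 1 schedule, and does not mention Table 16, the Part 2 schedule.

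**Protocol 1.4** names QTc prolongation and tremor as the key nonclinical findings and introduces its response with "we will implement the following monitoring procedures". For ECGs that the investigator interprets, signs and dates, it lists ventricular rate, PQ or PR, QRS and QT, ending: "QT interval (corrected and uncorrected) will be noted on the case report form (CRF". There is no AE condition.

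**SAP 6.12.4** tabulates observed values and changes from baseline for heart rate, PR, RR, QRS, QT, QTc, QTcB and QTcF by study part, period and treatment group. SAP 6.2.7 averages replicate continuous ECG values. Table 14.3.7.9 is the planned output. SAP 6.12.5 covers Holter only as a listing of collection data.

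**Holter.** Protocol 6.9.7 states: "Part 2 of the study will not have cardiac Holter monitoring". Appendix 6 repeats this for Part 2, and Appendix 5 excludes Holter and telemetry from the enteric-capsule repeat cohort. Yet Table 9 footnote f says "All safety ECGs on Day 1 and Day 2 will be extracted from a continuous 12 lead Holter recording at discrete timepoints", with no exception for that cohort, and Table 16 footnote e carries the same sentence into Part 2.

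**The concern.** Two current protocol sections give opposite recording rules for the same investigator-read tracings, and neither is given precedence. The SAP assumes the rule in Section 1.4. Section 7 of the SAP reports no change from the protocol's planned analyses, so the conflict goes unacknowledged.

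At stake is a planned safety output that serves the primary safety objective and concerns one of the two findings that shaped the monitoring. Under 6.9.6, Table 14.3.7.9 would receive post-dose interval values only where an AE had prompted someone to note them. Summary statistics from values selected in that way would not describe the treatment group. Changes in QTcF too small to be an AE, which a descriptive table is meant to show, would be missing.

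**Working it through.** The plan states no figure on this point, so the check is a comparison of texts and a count.

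**1. Do the two protocol rules cover the same ECGs?** Section 1.4 describes ECGs read and signed by the investigator or designee, then introduces Holter separately as an additional measure. Section 6.9.6 describes on-site review by the same people. Section 1.4 therefore cannot be confined to Holter extractions, and the conflict is real.

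**2. Which rule does the SAP need?**

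| Planned output | Needs | Available post-dose under 6.9.6 |
|---|---|---|
| Table 14.3.7.10, overall interpretation | Interpretation | Yes |
| Table 14.3.7.9, descriptive statistics | Intervals at each time point | Only as part of an AE |

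**3. Is there another QT source?**
- Part 1 cohorts with Holter: partly. Table 9 footnote f takes Day 1 and Day 2 safety ECGs from the Holter, and the Dose Escalation Review states: "ECG data will be analyzed in a blinded fashion and unblinded by ECG vendor in order to be presented by treatment group in aggregate". This SAP, however, contains no table of Holter intervals.
- Part 2 and Cohort 3b: no. Holter is excluded, so the footnote sentences about Holter extraction cannot operate. Safety ECGs continue, in Part 2 through Table 16 footnote d and in Cohort 3b because Appendix 5 leaves other procedures unchanged.
- Part 1 Holter data do not stand in for Part 2. The only fed condition in Part 1 is 1200 mg suspension (SAP 6.3). Part 2 gives 1800 mg SR fed and 2000 mg IR fasted and fed.

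**4. How many administrations rely on safety ECGs alone?**
- Cohort 8: 24 (Protocol 6.1).
- Cohort 9: 6 planned, minimum 4 (Protocol Section 3).
- Cohort 3b: 4, from Table 2, "Single dose of 300 mg (TBI-223 in oral enteric capsules) (n=4"; the minimum in Appendix 5 is 6.

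Planned: 24 + 6 + 4 = **34**. Low end: 24 + 4 + 4 = **32**. High end: 24 + 6 + 6 = **36**.

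**5. Share of the SAP displays.** The treatment labels in SAP 6.3 give 8 groups (Part 1 fasted) + 2 (Part 1 fed) + 1 (capsule) + 4 (Part 2 Period 1) + 1 (Part 2 Period 2) = 16. Those without Holter are 1 + 4 + 1 = 6.

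**6. What survives under 6.9.6?** Exclusion criterion 13 needs numeric QTcF at screening, Day -1 and Day 1 pre-dose, so pre-dose values must be derived in both parts. Stopping rule 3, "Two or more subjects develop drug-related QTcF prolongation greater than or equal to 500 msec or a change from baseline greater than 60 msec", and the ECG follow-up rule in the schedule footnotes need post-dose QTcF to be read. It can be read from the printout. What is missing is the entry of those readings for analysis.

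**The case against.** The strongest reply is that the site probably records the intervals. The SAP was written against protocol version 3.0 and Protocol Clarification Letter No. 4. It averages replicate ECG values and asks for QTcB and QTcF, which suggests that its authors expected interval fields on the CRF. This may well be right and cannot be excluded, but it does not reconcile the two protocol sections.

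Three stronger readings are tempting, and the documents support none of them.

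- **That QT data were lost.** Neither the CRF nor the clarification letter is available to us. The tracings are printed and reviewed, so the values can be recovered even if they were not entered.
- **That subjects were unprotected.** The QTcF criteria can be applied from the printout. Section 1.4 makes clinically significant ECG abnormalities AEs, for which 6.9.6 does allow intervals to be noted.
- **That the interval table would be empty throughout, or empty of everything except heart rate.** Eligibility already requires pre-dose QTcF, and Part 1 has a Holter source. Nothing in 6.9.6 says that heart rate is noted, so no count of affected variables can be built on that.

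One limit also stands. The ECG row of Table 16 is missing from the text we worked from, so the Part 2 post-dose ECG times could not be checked. The footnotes show that safety ECGs are scheduled.

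**Conclusion.** The point holds as a contradiction within the protocol that, on one of its two readings, defeats a planned SAP output. If 6.9.6 governs, post-dose interval values and changes from baseline that are not part of an AE would not be entered for analysis. The effect is greatest in Part 2 and Cohort 3b, where no other scheduled post-dose QT source exists: 34 planned administrations, range 32 to 36.

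We are confident of the contradiction. The consequence is conditional on the site having followed 6.9.6. It is a recording gap that can be repaired from paper, not a failure of subject protection. We give no estimate of how many subjects might show QTcF prolongation, because the documents offer no basis for one. The matter should be corrected because the remedy is small and the output concerns a safety signal that the protocol itself singles out.

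**What to change.** 1. In Protocol 6.9.6, replace the sentence on recording with: *Heart rate, PR, RR, QRS, QT and QTcF (QTcB derived) from every safety ECG in Part 1 (including Cohort 3b) and Part 2 will be recorded on the CRF.* Cite Table 16 alongside Table 9.
2. Delete the Holter-extraction sentence from Table 16 footnote e, and except Cohort 3b from the same sentence in Table 9 footnote f.
3. For cohorts already dosed without Holter, transcribe the intervals from the printed tracings if the CRF does not already hold them.

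The change should stop at recording. A clause requiring comparison with the SAP 6.2.2 baseline would go too far. That baseline is the last value before dosing, usually a single ECG because triplicates are confined to screening, Day -2, Day -1 and 48 hours. The clause would therefore tie the 60 msec criterion to a noisier reference that the protocol does not specify. Removing the leftover Day -2 triplicate from Table 16 footnote d is worthwhile but editorial only.

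The cost is one sentence, two footnote edits, CRF fields if they are absent, and a small amount of data entry. No procedure, reader or threshold changes.
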